	Appendix	
Sir	nple Clinical Colitis Activity Index (SCCAI)	27

1 List of Abbreviations

Abbreviation	Abbreviation definition
CMI	Cell mediated immunity
ELISPOT	Enzyme linked immunospot
IBD	Inflammatory Bowel Disease
ΙΕΝγ	Interferon gamma
HZ	Herpes Zoster
SCCAI	Simple Clinical Colitis Activity Index
TNF	Tumor necrosis factor
UC	Ulcerative Colitis
VZV	Varicella Zoster virus

2	Protocol	l Summary

_ Trococor Sammary	
Title:	Immunogenicity of herpes zoster subunit vaccine in ulcerative
	colitis patients treated with tofacitinib
Population:	UC patients on one of four treatment regimens as standard of care,
	who receive the Shingrix VZV vaccine, 100 patients, male + female,
	≥18 years old, no vulnerable populations
Intervention:	Each participant will be given two doses (0.5ml each) of the Shingrix
	vaccine, administered intramuscularly according to the following
	schedule: A first dose at Month 0 followed by a second dose
	administered anytime between 2 and 6 months later. The study
	population will generally include adult outpatient subjects with UC.
Objectives:	Change in CMI and VZV antibody concentration between pre-
•	immunization and at 1 month and 6 months post-immunization.
	Also monitoring for vaccine adverse effects over this time.
Design/Methodology:	Observational study without randomization and 4 study arms:
	Tofacitinib (10mg by mouth twice daily) monotherapy VS Anti-TNF
	monotherapy (adalimumab, golimumab, infliximab) VS Anti-TNF
	therapy with a thiopurine (6-mercaptopurine or azathioprine) VS no
	therapy or 5-aminosalicylates. Blood samples collected at clinic
	visits at enrollment, 1 month post-immunization, and 6 months
	•
	post-immunziation. If subject requires serologic confirmation of
	past VZV infection, an additional clinic visit 1 week after enrollment
	will be needed to follow-up on results of a confirmatory serology
	test.
Total Study Duration:	2 years.
Subject Participation Duration:	8-12 months.

3 Background/Rationale & Purpose

3.1 Background Information

Ulcerative colitis, a subset of inflammatory bowel disease, is a chronic inflammatory state of the gastrointestinal tract. Patients with IBD are at increased risk for developing infections including shingles with the Herpes Zoster virus as a result of their underlying disease regardless of immunosuppression. Studies have shown that those with IBD have an almost two-fold increased risk of HZ compared to agematched controls¹. Treatment with an immunosuppressant such as tofacitinib further increases this risk, as seen in patients with rheumatoid arthritis and psoriasis^{2,3}. Since most IBD patients are treated with systemic immunosuppressants, an independent risk factor for HZ, the live attenuated HZ vaccine was not recommended. However, the release of the new inactivated HZ vaccine, Shingrix (GlaxoSmithKline, Brentford, UK), presents new opportunities for preventive care.

Tofacitinib citrate (Xeljanz) is a Janus kinase inhibitor developed for the treatment of inflammatory diseases such as rheumatoid arthritis and psoriasis. The drug was approved in May 2018 by the FDA for the indication of moderate-to-severe UC but has been used off-label in various clinical settings. Shingrix is a new adjuvanted recombinant vaccine approved by the Food and Drug Administration for the prevention of herpes zoster in adults 50 years of age and older, and should be safe to administer in IBD patients. Though research has shown that patients with IBD on immunosuppression have an impaired immune response to vaccination as compared with non-immunosuppressed subjects and healthy controls⁴, the data on efficacy using the Shingrix vaccine appears promising even in severely immunocompromised hosts⁵.

Known risks include documented local and general reactions to the Shingrix vaccine as well as bruising or pain at the site of venipuncture. Potential benefits include vaccination to HZ as a result of receiving the Shingrix vaccine.

This study will be conducted in compliance with the protocol, applicable regulatory requirements, and BMC/BU Medical Campus Human Research Protection policies and procedures.

3.2 Rationale and Purpose

A study showing a lower risk of developing shingles in tofacitinib-treated patients who receive Shingrix will take years to complete. However, demonstrating a robust immune response to Shingrix may be used as a surrogate for a reduced risk of developing shingles and might alleviate prescribers' concerns regarding the use of tofacitinib.

This proposal will evaluate the immunogenicity of the new herpes zoster subunit vaccine in UC patients on tofacitinib monotherapy compared to those other therapies for UC. We will evaluate if the cell-mediated immunity to VZV is increased with immunization. Reactivation of VZV results in HZ, and strong cell mediated immunity prevents reactivation of HZ^{6,7}.

Our primary goal is to evaluate the immunogenicity of the herpes zoster subunit vaccine by obtaining pilot data to inform larger immunogenicity studies in the future. We will compare the VZV-specific T cell response (cell mediated immunity) prior and after immunization with the herpes subunit vaccine in IBD

patients aged 18 and older. T cell response is critical in preventing reactivation of VZV and will be measured using an IFNy ELISPOT, the standard measure of CMI to VZV⁸.

4 Objectives

4.1 Study Objectives

The primary objective of the study is to determine the immunogenicity of the herpes zoster subunit vaccine in ulcerative colitis patients on tofacitinib monotherapy compared to those on anti-tumor necrosis factor monotherapy, combination treatment with an anti-TNF agent and a thiopurine, and UC patients on 5-aminosalicylates or off therapy. Participants will be receiving the UC treatment regimens as standard of care prior to enrollment into the study. Immunogenicity will be evaluated by measuring humoral and cell mediated immunity in UC patients on tofacitinib who receive the two-dose herpes zoster vaccine. We will evaluate short term immunogenicity at one month after the second vaccination dose and sustained immunogenicity at 6 months post vaccination.

The central hypothesis of this proposal is that UC patients on tofacitinib will mount an adequate response to the Shingrix vaccine. We expect that the response will be slightly diminished compared to non-immunosuppressed IBD patients, comparable to those on anti-TNF monotherapy therapy and superior to those on anti-TNF therapy in combination with a thiopurine.

The immune response to the Shingrix vaccine has been shown to be >90% in healthy patients⁹. It is wellknown that IBD patients on immunosuppression, especially combination therapy (TNF plus an immunomodulator), have an impaired immune response to vaccination as demonstrated by the prospective clinical trial by Melmed et al⁴ and several others¹⁰. Therefore, we anticipate a diminished response to Shingrix in patients on TNF therapy in combination with a thiopurine. We are excluding patients receiving methotrexate as its utility in treating UC patients is limited. On the other hand, the response to inactivated vaccines in patients on anti-TNF monotherapy are conflicting in that some studies show a diminished response to the inactivated Hepatitis B vaccine^{11,12} and the influenza vaccine¹³ for instance where other trials showed an immune response that was comparable to healthy controls, in patients receiving tetanus and pertussis vaccinations 10. Lastly, aminosalicylates are used to treat mild-to-moderate UC and have no effects on the immune system. While we recognize that this population differs from our study population, it is standard practice to include such patients in clinical trials as their response to vaccine is expected to be comparable to non-IBD patients and they serve as important controls. Thus, we postulate that IBD patients off therapy or on 5-aminosalicylates, will respond most favorably to vaccination, followed by patients on anti-TNF monotherapy and lastly, patients on combination therapy with a thiopurine.

With regard to tofacitinib monotherapy, the proportion of patients achieving vaccine response to PPSV-23 was lower in the tofacitinib group but may have been confounded by methotrexate¹⁴. The responses were 68.4%, 61.8 and 31.6% in the placebo group, tofacitinib monotherapy group and tofacitinib + methotrexate group respectively. In contrast, a similar proportion of patients receiving tofacitinib and placebo achieve adequate responses to the influenza vaccine. Another recent study showed that patients on tofacitinib 10mg BID demonstrate 60% response to the tetanus vaccine, defined as a 4-fold increase in antibody titers¹⁵. Similar response rates are seen in the IBD population on TNF-monotherapy¹⁰. IBD patients on tofacitinib will likely have failed biologic therapy and may be on short-

term steroids which may affect their immunogenicity to vaccines. Thus, we anticipate that IBD patients on tofacitinib monotherapy will have a slightly diminished response to Shingrix compared to non-immunosuppressed IBD patients (or those on aminosalicylates) but that the response will be comparable to patients on anti-TNFs alone and superior to patients on combination treatment with a thiopurine.

The secondary objectives of the study are to monitor for vaccine-related adverse events and change in UC disease activity throughout the duration of the study in order to obtain other practical information that may help inform providers in clinical decision making regarding the use of Shingrix and/or tofacitinib.

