4.2 Study Outcome Measures

4.2.1 Primary Outcome Measures

Change in the immunogenicity of the herpes zoster subunit vaccine in UC patients. Immunogenicity will be assessed by the change in CMI as measured by ELISPOT from pre-immunization to 1 month after receiving second dose of booster vaccine post-immunization. ELISPOT is an enzyme-linked assay for detecting and enumerating cytokine-producing lymphocytes. A colored spot indicates a cell producing IFNy. Each well will be inspected and cytokine-producing cells will be counted using AID® imaging system. Any well with more than 300 spots will be considered too numerous to count and reported as >300 cells/well. It will be measured from pre-immunization to 1 month after receiving second dose of booster vaccine post-immunization.

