11.6 Sample Size Determination

We will recruit a total of 100 subjects, anticipating 25 subjects per study arm. Assuming an attrition rate of 20%, our goal final sample size is 80 subjects, with 20 subjects in each arm.

Power calculations revealed that >200 patients per study arm would be needed to estimate small differences in efficacy, assuming a 10% difference between tofacitinib monotherapy patients and non-immunosuppressed IBD patients for instance. Since there are no previous data on vaccine responses to HZ in IBD patients from which we can calculate power estimates, sample size has been determined by feasibility of recruitment at various sites. Our goal is to perform exploratory data analyses and derive estimates of vaccine response results in this population to power future studies.

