11.7 Statistical Methods

Summary statistics including the mean, median, SD and range will be presented for continuous variables and N (%) will be presented for categorical variables, overall and by IBD group. Comparisons across groups on baseline demographic and clinical characteristics will be performed using ANOVA for continuous variables and the chi-squared test for categorical variables. Any comparison across groups significant at the p< 0.1 level will be considered for a multivariable-adjusted model for the primary outcome.

For the primary outcome of percent change in cell-mediated immunity from baseline to one-month post-immunization, we will first compare the tofacitinib alone group (Group A) to the non-immunosuppressive group (Group D) using a contrast statement as part of an ANOVA model. Comparisons of Group A with Groups B and C will use the same methodology. The same methodology will be used to compare the secondary outcomes among the four IBD groups in a similar manner. Any imbalances in baseline characteristics will be incorporated into a multivariable regression model to determine the adjusted differences between groups.

Incidence of adverse events will also be compared between groups using the chi-squared or Fisher's Exact test, as appropriate. A value of p< 0.05 is considered statistically significant, except where otherwise noted.

12 Ethics/Protection of Human Subjects

This study is to be conducted according to applicable US federal regulations and institutional policies (which are based in federal regulations, guidance, and ICH Good Clinical Practice guidelines).

This protocol and any amendments will be submitted to the Boston Medical Center and Boston University Medical Campus IRB, for formal approval of the study conduct. The decision of the IRB concerning the conduct of the study will be made in writing to the investigator. A copy of the initial IRB approval letter will be provided to the sponsor before commencement of this study.

All subjects for this study will be provided a consent form describing this study and providing sufficient information for subjects to make an informed decision about their participation in this study. The consent form will be submitted with the protocol for review and approval by the IRB. The consent of a subject, using the IRB-approved consent form, must be obtained before that subject is submitted to any study procedure. Consent will be documented as required by the IRB.

13 Literature References

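### The central hypothesis of an adequate response on tofacitinib, and the aim of showing that CMI rises after vaccination, have no inferential analysis, and adequate is undefined

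*Combined protocol and SAP*

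**What the plan says.** Section 4.1 gives the central hypothesis as "UC patients on tofacitinib will mount an adequate response to the Shingrix vaccine". The expected ordering against the other three groups follows in a separate sentence. Section 3.2 states: "We will evaluate if the cell-mediated immunity to VZV is increased with immunization".

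The primary outcome in Section 4.2.1 is continuous: "Immunogenicity will be assessed by the change in CMI as measured by ELISPOT from pre-immunization to 1 month after receiving second dose". The antibody outcomes in Section 4.2.2 are also continuous changes. Section 11.5 restates the hypotheses only as comparisons of tofacitinib with the other groups, and adequacy does not appear there. Section 11.6 says that the sample size was set by feasibility and that the goal is to "derive estimates of vaccine response results in this population to power future studies".

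For analysis, Section 11.7 compares Group A with Group D on percent change in CMI "using a contrast statement as part of an ANOVA model". It adds: "Comparisons of Group A with Groups B and C will use the same methodology". Baseline imbalances go into a regression. The same section begins: "Summary statistics including the mean, median, SD and range will be presented for continuous variables", overall and by group. It mentions no confidence interval and no within-group test. The one explicit responder rule in the documents, "defined as a 4-fold increase in antibody titers", is in Section 4.1 and describes a cited study of tetanus vaccine.

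**The concern.** The central hypothesis and the aim in Section 3.2 concern one group before and after vaccination. The contrasts concern differences between groups. Groups A and D could differ little because both responded poorly, or differ clearly although both responded well. No result of the A-vs-D, A-vs-B or A-vs-C contrast therefore settles whether Group A's immunity rose, still less whether the rise was adequate.

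Section 3.2 hopes that a robust response will ease prescribers' concerns about tofacitinib. If the report has only contrasts and summary statistics without intervals, that claim has no pre-specified support. Any standard of adequacy would then have to be chosen after the results are known.

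**Working it through.** **1. Questions set beside analyses.**
- Does CMI rise after vaccination (3.2)? Section 11.7 has no within-group test or interval. At most it gives a by-group mean and SD of the change.
- Is the response on tofacitinib adequate (4.1)? No criterion is stated in any section, and no analysis is tied to the word.
- How does A compare with D, B and C (4.1, 11.5)? Section 11.7 has contrasts for exactly these pairs.
- What is the size of vaccine response, for future planning (11.6)? Section 11.7 has descriptive statistics without intervals and does not expressly apply them to the post-vaccination outcome.

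**2. The plan's own figures (11.6).** 100 × (1 − 0.20) = 80 evaluable, and 80 / 4 = 20 per arm, as stated. The figure of more than 200 per arm for a 10% difference comes with no base rate and no power. If it is read as two proportions, 0.90 vs 0.80, two-sided 0.05, 80% power, then n = [1.96 × √(2 × 0.85 × 0.15) + 0.842 × √(0.90 × 0.10 + 0.80 × 0.20)]² / 0.10² = (0.990 + 0.421)² / 0.01 ≈ 199 per arm, or 219 with continuity correction. Other base rates give 141 (95% vs 85%) to 388 (60% vs 50%). The figure is consistent with a response rate but does not establish one.

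**3. What a within-group interval would deliver.** For a mean log rise in n = 20, the 95% half-width is t(0.975; 19) / √20 = 2.093 / 4.472 = 0.468 SD, where SD is that of the individual log rises. The lower limit of the geometric mean fold rise therefore exceeds 1 when the observed mean log rise is above 0.468 SD. A paired test has 80% power for a true rise of 0.66 SD. With all 25 evaluable, the half-width is 0.413 SD.

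**4. What a responder proportion would deliver.** Exact (Clopper-Pearson) 95% intervals at n = 20 are 68.3% to 98.8% for 18/20 and 36.1% to 80.9% for 12/20.

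**5. What a non-significant contrast would say.** For a two-sample t-test with 20 per arm and two-sided 0.05, the difference detectable with 80% power is 0.91 SD. Power is 0.095 at 0.2 SD and 0.152 at 0.3 SD. If tofacitinib is only slightly worse than Group D, as the protocol expects, non-significance is the likely result and says almost nothing about adequacy.

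**The case against.** The best defence is that the documents make the hypothesis operational through comparison. The primary objective is comparative, Section 11.5 lists only comparisons, and the contrasts match those pairs. The study is exploratory and sized by feasibility, so one undefined adjective in the objectives may look minor. This partly stands, because the comparative hypotheses do have an analysis. It does not cover the central hypothesis as worded, or the aim in Section 3.2. Exploratory status strengthens the case for intervals, since estimation is the declared goal.

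Four stronger readings are tempting, and the documents do not support them.
- A reader might infer that vaccine response is not estimated at all. Section 11.7 provides by-group summary statistics, and percent change is itself a before-and-after measure. If the summaries cover the outcome, they give a mean and SD from which a future continuous-endpoint study could be sized.
- A reader might infer that Section 11.6 powers on a response rate that the plan then omits. The section speaks of a 10% difference in efficacy and names no binary endpoint, so this is plausible but assumed.
- A reader might infer that the sponsor means to read a non-significant A-vs-D contrast as adequacy. No section says so, and the protocol predicts that A will be lower than D.
- A reader might take the 4-fold rule as this study's responder definition. It is an antibody rule from another vaccine, while the primary outcome is ELISPOT CMI.

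The low power in step 5 is largely conceded in Section 11.6 and is not a separate fault here.

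**Conclusion.** The concern holds in a limited form. The central hypothesis and the before-and-after aim have no inferential analysis, and adequate has no definition. The planned contrasts remain valid for the comparisons in Section 11.5, and by-group description is planned.

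The gap can be closed with data already being collected. At 20 per arm the within-group mean log rise would be known to about ±0.47 SD, and 18/20 responders would give 68% to 99%. These figures assume 20 evaluable patients per arm, two-sided 95% intervals, roughly normal log rises and no censored values. Wells reported only as above 300 would alter the precision. The documents give no SD for the log rise, so the half-width cannot be turned into a fold-rise range.

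The change should be made before assay results are seen.

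**What to change.** In Section 11.7:
- For each group, report the geometric mean fold rise in CMI and in VZV antibody from baseline to 1 month and to 6 months, with 95% CIs.
- Treat ELISPOT wells reported as above 300 as censored. A censored post-vaccination count makes the observed rise a lower bound, and a censored baseline makes it an upper bound. Entering 300 as an exact value hides this.
- State that CMI is increased in Group A only if the lower limit at 1 month exceeds 1. This shows a rise and does not by itself show adequacy.
- State that a non-significant A-vs-D contrast will not be read as evidence of an adequate response.

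In Section 4.1, either define adequate by a justified criterion fixed before assay results are seen, or drop the word and state the aim as by-group estimation of the rise.

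Optionally, report by group the proportion with at least a 4-fold antibody rise with an exact 95% CI, labelled descriptive because the cut-off comes from another vaccine.

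The cost is statistical wording, two short tables and a fold-rise scale beside percent change. No extra samples or visits are needed.

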4.2 Study Outcome Measures

4.2.1 Primary Outcome Measures

Change in the immunogenicity of the herpes zoster subunit vaccine in UC patients. Immunogenicity will be assessed by the change in CMI as measured by ELISPOT from pre-immunization to 1 month after receiving second dose of booster vaccine post-immunization. ELISPOT is an enzyme-linked assay for detecting and enumerating cytokine-producing lymphocytes. A colored spot indicates a cell producing IFNy. Each well will be inspected and cytokine-producing cells will be counted using AID® imaging system. Any well with more than 300 spots will be considered too numerous to count and reported as >300 cells/well. It will be measured from pre-immunization to 1 month after receiving second dose of booster vaccine post-immunization.

4.2.2 Secondary Outcome Measures

- #1: **Sustained T cell response.** Sustained change in CMI at 6 months will be assessed after receiving a second dose of booster vaccine post-immunization.
- #2: **Change in antibody response.** Antibody response will be measured by the change in VZV antibody concentration from pre-immunization to 1 month post-immunization. VZV antibody concentrations in serum samples will be measured using a commercially available ELISA kit (Abnova, Walnut, CA) according to the manufacturer's instructions. This quantitative VZV antibody concentration will be in addition to the one that may be needed to determine previous varicella infection for study eligibility.
- #3: **Sustained antibody response.** Sustained change in VZV antibody concentration at 6 months after receiving a second dose of booster vaccine post-immunization will be assessed.
- #4: Vaccine adverse effects. Patients will either receive phone calls from study personnel or be evaluated at clinic visits to ascertain vaccine-related adverse effects at months 1, 2, 3 (1 month post-immunization), and 8 (6 months post-immunization). Our study is underpowered to measure differences in adverse effects between groups. Adverse event data will be reported.
- #5: Change in UC disease activity. The SCCAI will be used to measure disease activity. It is a questionnaire with six subscore topics with scores defined by UC signs and symptoms from 0 to 4 for a

range of scores from 0 to 17. Total scores are interpreted as: Remission = score of 0 to 4 points, Mild Activity = score of 5 to 7 points, Moderate Activity = Score of 8 to 16 points, and Severe Activity = Score of > 16 points.

5 Study Design

The clinical trial will be a Phase IV multi-center non-randomized non-blinded observational study. As part of standard of care for this patient population and therefore outside of the study, each participant will be given two doses (0.5ml each) of the Shingrix vaccine, administered intramuscularly according to the following schedule: A first dose at Month 0 followed by a second dose administered anytime between 2 and 6 months later.

The study population will include adult outpatient subjects with UC. The study will compare the immunogenicity and VZV antibody concentrations in the participants who will be stratified into one of 4 arms (each containing 25 subjects) based on their medical regimen, which is also standard of care and will be established outside of the study:

- Group A UC patients on tofacitinib monotherapy.
- Group B UC patients receiving anti-TNF monotherapy (adalimumab, golimumab, infliximab).
- Group C UC patients on an anti-TNF agent and a thiopurine (6-mercaptopurine, azathioprine).
- Group D UC patients on non-immunosuppressive therapy or 5-aminosalicylates.

As part of the actual study, 3 total blood samples will be collected. Samples will be collected at clinic visits at the time of enrollment, 1-month post-immunization, and 6 months post-immunization. Patients will also be asked to report change in their UC symptoms and any adverse effects to the vaccine at each clinic visit and follow-up phone calls.

6 Potential Risks and Benefits

